12.6.2.2 Sensitivity Analyses

As a sensitivity analysis, the time to first occurrence of virologically-confirmed COVID-19 case of any severity according to the primary case definition is analyzed. Calculation of the time to first occurrence and censoring rules are applied according to Section 10.11.

Kaplan-Meier (KM) estimates for the probability of not developing COVID-19 (hereafter referred to as "survival") are computed for each vaccine group. Estimates for Q1, median and Q3 of the survival times are presented. A log rank test comparing the vaccine groups is performed. The summaries are provided by vaccine group and by age group and vaccine group.

KM curves by vaccine group are presented, displaying the estimated survival probabilities over time. These figures are also repeated by age group and vaccine group.

A Cox Proportional Hazard model is used to model the time to first occurrence of virologically-confirmed COVID-19 cases according to primary case definition (any severity). The model includes the vaccine group as a factor and is adjusted for the stratification factors age at baseline (18 to 60 and ≥ 61 years) and country. The estimated Hazard Ratios (HR) for the CVnCoV vaccine group versus placebo and corresponding 95% CI as well as the 97.5% CI is presented. The CIs are derived based on the Wald test. This analysis is repeated by age group, but the corresponding model does not include the age group as a factor.

A subgroup analysis of region (LATAM vs EUROP) on the primary endpoint is also performed.

These sensitivity analyses are performed on the EAS.

12.6.3 Secondary Efficacy Analyses

12.6.3.1 Key Secondary Efficacy Analyses

The key secondary efficacy endpoints in this trial are:

- The occurrence of first episodes of virologically-confirmed moderate to severe cases of COVID-19 meeting the case definition for the primary efficacy analysis
- The occurrence of first episodes of virologically-confirmed severe cases of COVID-19 meeting the case definition for the primary efficacy analysis. For details on the definition of moderate and severe COVID-19 cases see 10.7.3.
- The occurrence of first episodes of virologically-confirmed (RT-PCR positive) cases of COVID-19 of any severity meeting the case definition due to infection with “wild type” and “Alpha” SARS-CoV-2 strains in SARS-CoV-2 naïve subjects. For details on the definition of VOC see Section 10.7.5

For the above endpoints, the analysis approach as described for the primary endpoint in Section 12.6.2.1 are conducted in a similar manner. For details regarding events to be considered in each analysis and for calculation of follow-up time, refer to Section 10.13.

As the key secondary efficacy endpoints are not part of the interim analysis, the significance level does not require an adjustment and – following successful demonstration of efficacy in the primary endpoints - the full 5% level of significance is used for statistical testing. Different success thresholds are also defined for these endpoints. Consequently:

- Efficacy based on moderate to severe cases of COVID-19 is demonstrated if the LL of the exact two-sided 95% Pearson-Clopper CI for the VE based on moderate to severe cases is above 20%
- Efficacy based on severe cases of COVID-19 is demonstrated if the LL of the exact two-sided 95% Pearson-Clopper CI for the VE based on severe cases is above 10%.
- Efficacy based on first episodes of virologically-confirmed (RT-PCR positive) cases of COVID-19 of any severity meeting the case definition due to infection with “wild type” and “Alpha” SARS-CoV-2 strains in SARS-CoV-2 naïve subjects is demonstrated if the LL of the exact two-sided 95% Pearson-Clopper CI for the VE based on severe cases is above 30%.

Note that the hierarchical testing procedure outlined in Section 12.6.1 has to be considered when assessing if efficacy has been demonstrated based on each of the four key secondary efficacy endpoints.

The following is presented for the key secondary efficacy analyses:

- Number and percentage of subjects with a respective case,
- Total follow-up time (years) in each vaccine group,
- Calculated proportion of cases coming from the CVnCoV group among all cases (p),
- Ratio of total follow-up time of subjects in the CVnCoV group over the total follow-up time of subjects in the placebo group (r),
- Estimated VE based on p and r,
- 95% CIs for p and VE.

The analyses of the key secondary efficacy endpoint is performed on the EAS.

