10.3.5.2 Secondary Efficacy Endpoints Analyses

Statistical testing of the 3 key secondary efficacy endpoints will be performed according to the conditional hierarchical testing procedure using the order defined in the objective/endpoints sections. Consequently:

- Efficacy of CVnCoV in regard to moderate and severe cases will be demonstrated only if there is successful demonstration of the primary efficacy objective.
- Efficacy of CVnCoV in regard to severe cases will be demonstrated only if there is successful demonstration of the primary efficacy objective and the key secondary objective on moderate and severe cases.
- Efficacy of CVnCoV in regard to (RT-PCR positive) cases of "wild type" (i.e., WT/D614G lineages A.1/B.1 without VOC B.1.1.7 [Alpha], B.1.351 [Beta], B.1.429 [Epsilon]) and "UK" (B.1.1.7 [Alpha]) will be demonstrated only if there is successful demonstration of the primary efficacy objective and the key secondary objective on moderate and severe cases and severe cases.

Otherwise, these endpoints will be analyzed as exploratory endpoints without success criteria testing.

To assess the efficacy in the prevention of "wild type" (i.e., WT/D614G lineages A.1/B.1 without VOC B.1.1.7 [Alpha], B.1.351 [Beta], B.1.429 [Epsilon]) and "UK" (B.1.1.7 [Alpha]) cases, moderate to severe, severe disease and asymptomatic infections, similar analyses to those performed on the primary efficacy endpoint will be performed. The efficacy will be demonstrated if the lower limit of the exact 2-sided 95% CI of VE is above 30% for "wild type" (i.e., WT/D614G lineages A.1/B.1 without VOC B.1.1.7 [Alpha], B.1.351 [Beta], B.1.429 [Epsilon]) and "UK" (B.1.1.7 [Alpha]) cases, 20% for moderate to severe disease, 10% for severe disease and above 0% for asymptomatic infections.

Other secondary efficacy endpoints will be analyzed similarly to the primary efficacy endpoint but no formal testing will be performed for those endpoints. For efficacy after the first dose, the time to first-occurrence of virologically-confirmed COVID-19 (date of symptom onset) will start after the first vaccination. The BoD will be analyzed using 2 different scoring systems. Both BoD scoring systems place more weight on efficacy against severe COVID-19 or severe disease as reflected by hospitalization or death. In addition, VE and associated CI will be calculated for each of the BoD categories.

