8.7.2 Sample Size Considerations for the Key Secondary Objectives

For the key secondary efficacy objective evaluating the prevention of virologically-confirmed moderate to severe cases of COVID-19, a lower number of cases has accrued at the time of final primary efficacy analysis compared to the primary endpoint. If one third of cases of any severity are moderate to severe, then 53 moderate to severe cases can be expected when the total number of COVID-19 cases is 160. The trial then has 91.5% power to obtain a lower limit (LL) of the 95% CI of the VE above 20% when assuming the true VE is 70%.

For the key secondary efficacy objective evaluating the prevention virologically-confirmed severe cases of COVID-19 an analysis of a large database by Verity et al. [2], suggests approximately 20% of COVID-19 cases can be clinically defined as severe or critical, the latter requiring intensive care.

With 32 cases of severe COVID-19 (20% of 160 cases), the trial has 81.5% power to detect a LL of the 95% CI of the VE above 10% when assuming the VE is 70%. The power increases to 91% if the VE against severe cases is 75%.

For the key secondary endpoint the prevention of first episodes of virologically-confirmed cases of COVID-19 of any severity caused by "wild type", if 50% of COVID-19 cases of any type are "wild type" and "Alpha", then 80 such cases can be expected when the total number of COVID-19 cases is 160. The trial then has 90.7% power to obtain a LL of the 95% CI of the VE above 30% when assuming the true VE is 70%.

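### The SAP's success rule for the wild-type/Alpha key secondary endpoint is written on efficacy against severe cases, not on wild-type/Alpha cases

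*SAP*

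**What the plan says.** SAP 12.6.3.1 lists three key secondary endpoints: moderate to severe cases, severe cases, and "cases of COVID-19 of any severity meeting the case definition due to infection with" wild-type and Alpha strains. It then gives one success criterion for each.

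- **Severe cases (second bullet):** met if "the LL of the exact two-sided 95% Pearson-Clopper CI for the VE based on severe cases is above 10"%.
- **Wild-type/Alpha cases (third bullet):** met if "the LL of the exact two-sided 95% Pearson-Clopper CI for the VE based on severe cases is above 30"%.

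The same section says that, after success on the primary endpoint, "the full 5% level of significance is used for statistical testing". SAP 12.6.1 places these endpoints in a conditional hierarchy in the order listed, so wild-type/Alpha is tested last.

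The protocol's rule is different. Section 10.3.5.2 begins "The efficacy will be demonstrated if the lower limit of the exact 2-sided 95% CI of VE is above 30% for" and continues with wild-type and UK (Alpha) cases. It then gives the other bounds: "20% for moderate to severe disease, 10% for severe disease and above 0% for asymptomatic infections".

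SAP 8.7.2 takes half of the 160 planned cases, that is 80, to be wild-type or Alpha, and states: "The trial then has 90.7% power to obtain a LL of the 95% CI of the VE above 30"%, at a true VE of 70%.

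**The concern.** The third bullet opens with the variant endpoint and ends with a criterion on a different one. As written:

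- the severe endpoint carries two thresholds, 10% and 30%;
- the wild-type/Alpha endpoint has no criterion of its own;
- no wild-type or Alpha case enters the decision on wild-type/Alpha efficacy, except by also being severe.

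This is a confirmatory decision rule in an alpha-controlled sequence. Applied literally, the variant claim could be made or refused whatever the variant cases show, and the power stated in SAP 8.7.2 would not describe the test performed.

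**Working it through.** **1. Which rule do the other sections support?**

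| Place | What the third key secondary endpoint or its 30% bound refers to |
|---|---|
| Protocol 10.3.5.2 | 30% on wild-type/Alpha cases; 10% on severe disease |
| Protocol 10.1.2 and SAP 8.7.2 | 30% powered on 80 wild-type/Alpha cases |
| Protocol 4.3 and SAP 9.5 (estimands) | wild-type/Alpha cases |
| SAP 7.2.1 (objective), 9.2.1 (endpoint), 10.7.5 | wild-type/Alpha cases |
| SAP 6.2 (intended divergences from the protocol) | nothing on this point |
| SAP 12.6.3.1, third bullet | 30% on severe cases |

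Only the third bullet differs.

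**2. Method.** SAP 12.6.2.1 tests the share of cases in the CVnCoV group, p, with an exact binomial test, and SAP 12.6.3.1 carries the approach over. With equal follow-up (r = 1):

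- share at the margin m: p0 = (1 − m)/(2 − m)
- share at the true VE: p1 = (1 − VE)/(2 − VE)
- lower limit for VE: LL = 1 − UL/(1 − UL), where UL is the upper 95% Clopper-Pearson limit for p
- critical count c: the largest number of CVnCoV cases with LL > m
- power: P(X ≤ c) for X ~ Binomial(n, p1)

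**3. Reproduce the plan's figures.** For VE 70%, p1 = 0.3/1.3 = 0.2308. For VE 75%, p1 = 0.25/1.25 = 0.2000.

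| Endpoint | n | m | p0 | c | True VE | Power computed | Power stated |
|---|---|---|---|---|---|---|---|
| Moderate to severe | 53 | 20% | 0.8/1.8 = 0.4444 | 16 | 70% | 91.5% | 91.5% |
| Severe | 32 | 10% | 0.9/1.9 = 0.4737 | 9 | 70% | 81.5% | 81.5% |
| Severe | 32 | 10% | 0.4737 | 9 | 75% | 91.0% | 91% |
| Wild-type/Alpha | 80 | 30% | 0.7/1.7 = 0.4118 | 23 | 70% | 90.7% | 90.7% |

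All four agree. For wild-type/Alpha, 23 of 80 gives an observed VE of 1 − 23/57 = 59.6%, UL = 0.3995 and LL = 33.5%. With 24 of 80 the LL falls to 29.7%, so 23 is the cut-off.

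**4. The rule as written.** Severe cases n = 32 (20% of 160), m = 30%, p0 = 0.4118:

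- c = 7: observed VE 1 − 7/25 = 72.0%, UL = 0.3997, LL = 33.4%. With 8 of 32 the LL is 23.3%.
- Power is 53.4% at VE 70% and 69.8% at VE 75%.

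The stated 90.7% therefore comes from the 80 variant cases and cannot come from the 32 severe cases.

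**The case against.** The strongest reply is that this is a slip of wording and not a choice of analysis. The sentence starts by naming the variant endpoint, and the stray phrase repeats the bullet above it. The objective, endpoint, estimand and sample-size text all give the intended rule. SAP 12.6.3.1 also presents the VE and its 95% CI for each listed endpoint, so the variant estimate is produced in any case and anyone can hold it against the protocol's 30%. That stands, and it means the harm depends on literal application.

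Timing also limits the effect. SAP 12.6.1 places the key secondary analyses at the final primary efficacy analysis, which preceded SAP version 5.0, and plans no re-run at end of trial. It does leave open re-running some outputs because of the corrected unblinding dates at one site (AR009). The variant step is reached only after success on the three endpoints before it.

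The 53.4% describes a rule that was probably never intended, and it uses planned counts. Protocol 3.1.4 reports 228 cases. If the planned 20% severe share held (an assumption), that gives 0.20 × 228 = 45.6 severe cases. The literal rule would then have 66% power with 45 cases (c = 11) or 75% with 46 (c = 12) at VE 70%. The loss is smaller, but it is still a test of the wrong endpoint.

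None of this makes the sentence correct. SAP 6.0 says the document describes the methods of the final primary efficacy analysis, and SAP 6.1 says version 5.0 was written and approved by an unblinded team. In that setting a confirmatory rule should not have to be inferred.

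**Conclusion.** The concern holds. The third criterion in SAP 12.6.3.1 names the wrong endpoint and contradicts the protocol, the SAP's own power basis and the severe-case rule beside it. On the planned counts the intended rule has 90.7% power (at most 23 of 80), against 53.4% for the rule as written (at most 7 of 32), both at a true VE of 70%.

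These figures assume r = 1, 80 wild-type/Alpha cases and 32 severe cases. The documents do not report the actual severe or variant counts, so the 53.4% illustrates the literal reading and is not an estimate of what happened. The contradiction itself depends on none of these assumptions. It should be corrected; the practical consequence is limited because the intended rule is plain elsewhere and the main analysis was already done.

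**What to change.** In the third criterion of SAP 12.6.3.1, replace the reference to severe cases with a reference to cases due to wild-type and Alpha strains, keeping the 30% bound. The margin, the significance level and the 90.7% power do not change.

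Because version 5.0 was approved after unblinding, record the change in the SAP change history as a correction that restores the prespecified rule in protocol 10.3.5.2. State which rule was applied at the final efficacy analysis.

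Two related items should be corrected in the same edit: SAP 12.6.3.1 refers to four key secondary endpoints where three are listed, and Table 11 in SAP 10.13, to which that section points for follow-up time, has no row for the wild-type/Alpha endpoint.

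The cost is one phrase, one change-history entry and these two small corrections. No new data or analyses are needed if the protocol's rule was the one applied.

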12.6.3.2 Sensitivity Analyses

The sensitivity analyses described in Section 12.6.2.2 for the primary efficacy endpoint is also performed on the 3 key secondary efficacy endpoints.

12.6.3.3 Other Secondary Efficacy Analyses

Other secondary efficacy endpoints in this trial are:

- Occurrence of first episodes of virologically-confirmed cases of COVID-19 of any severity meeting the case definition for the primary efficacy analysis in subjects ≥ 61 years of age.
- BoD scores calculated based on first episodes of virologically-confirmed cases of COVID-19 of any severity meeting the case definition for the primary efficacy analysis.
- Occurrence of first episodes of virologically-confirmed cases of COVID-19 of any severity with symptom onset at any time after the first trial vaccination.

For the above endpoints, excluding BoD scores, the analysis approach as described for the primary endpoints in Section 12.6.2.1 is conducted in a similar manner, but no confirmatory testing is performed. For details regarding events to be considered in each analysis and for calculation of follow-up time, refer to Section 10.13.

The following is presented for the secondary efficacy analyses:

- Number and percentage of subjects with a respective case,
- Total follow-up time (years) in each vaccine group,
- Calculated proportion of cases coming from the CVnCoV group among all cases (p),
- Ratio of total follow-up time of subjects in the CVnCoV group over the total follow-up time of subjects in the placebo group (r),
- Estimated VE based on p and r,
- 95% CIs for p and VE.

For the BoD endpoints, the number and percentage of subjects in each category is summarized descriptively for both of the two scores.

Additionally, VE measures based on each of the calculated BoD Scores (referred to as “ VE_{BoD} ”) are derived. VE_{BoD} is defined as the relative reduction in the BoD score in the CVnCoV group compared to Placebo and is calculated as:

$$VE_{BoD} = 1 - \frac{SV}{SP}$$

Thereby, SV denotes the ratio of mean BoD score in the CVnCoV group and the mean follow-up time (years) in the CVnCoV group and SP denotes the ratio of mean BoD score in the Placebo group and the mean follow-up time (years) in the Placebo group (see Section 10.13).

The VE_{BoD} and corresponding 95% CI based on the Normal distribution are presented for each of the two BoD scores defined. The analysis tables also present the calculated mean BoD scores in the CVnCoV and Placebo groups and the total follow-up time (months) in each group.

The analyses of the other secondary efficacy endpoint of COVID-19 cases in subjects 61 years or older are performed on the EAS, thereby restricting to subjects with age at trial entry ≥ 61 years. This analysis is not repeated by age group.

The analysis of the other secondary efficacy endpoint of BoD categories is performed on the EAS.

The analysis of the other secondary efficacy endpoint COVID-19 cases after first vaccination is performed on the SAS, restricted to subjects with a negative baseline serology (see Section 10.6.1).

All secondary efficacy endpoints mentioned in this section are provided for the interim analyses and for the primary efficacy delivery.

All applicable cases available in the respective data cut are used for the respective analyses.

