10.2 Populations for Analyses

In the Safety Analysis Set (SAS), Safety Analysis Set 2 (SAS 2), and the Solicited AEs Safety Analysis Set (SASsol), subjects will be analyzed in the group they actually received (as "treated").

Following the "intent to treat" principle in the Efficacy sets and Per-Protocol Sets, subjects will be analyzed in the group to which they were randomized (as "randomized").

Additional populations that might be required for the analyses of the results from the open-label phase are of exploratory nature and will be defined in an extended SAP.

An authorized/licensed SARS-CoV-2 vaccine has become available during the trial and subjects can request to be unblinded. The censoring rules to avoid any bias for such subjects will be described in the SAP (randomized observer-blinded phase only).

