10.2.1 Safety Analysis Set (SAS)

The SAS will include all subjects randomized in Phase 2b or 3 who received at least 1 dose of CVnCoV or placebo.

The SAS will be the primary population for safety endpoints collected on all subjects (i.e., medically-attended AEs, AESI, AEs leading to withdrawal or trial discontinuation, and SAEs) and for efficacy objectives assessing efficacy after the first dose.

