9.6 Population Sets

In the Safety Analysis Set (SAS), the Safety Analysis Set 2 (SAS 2) and in the Solicited AEs Safety Analysis Set (SASsol), subjects are analyzed in the group they actually received (“as treated”). Based on the number of subjects receiving treatment not as randomized, selected efficacy analyses performed on the SAS “as treated” may be repeated on the SAS, analyzing subjects under the treatment they were actually randomized to.

If a subject received both the active vaccine and the placebo (i.e. at the two different vaccination timepoints or the same vaccination timepoint), subjects are analyzed in the active vaccine group for “as treated” analyses.

Following the intent-to-treat principle, in the Efficacy Sets and Per-Protocol Sets, subjects are analyzed in the group to which they were randomized (“as randomized”).

Any analyses using all randomized subjects are based on vaccination “as randomized”.

Clarifying notes regarding immunogenicity analyses: There are no analyses (tables or figures) performed on the full IS (only on the Per Protocol Immunogenicity [PPI] Set which is a subset of the IS). Listings based on the IS are displayed by actual treatment received. As described above, analyses on the PPI Set are performed “as randomized”. As correct treatment allocation is an eligibility criterion for any per protocol (PP) set in this study, “as randomized” and “as treated” are identical for PP sets.

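### Vaccine efficacy after the first dose is analysed as treated, with anyone given both products counted wholly as CVnCoV, and the as-randomised analysis is only optional

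*SAP*

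**What the plan says.** SAP 12.6.3.3 sets the population: "The analysis of the other secondary efficacy endpoint COVID-19 cases after first vaccination is performed on the SAS". Only those whose serology was negative at entry are kept. Protocol 10.2.1 makes the same choice, naming the SAS as the primary population for all-subject safety endpoints "and for efficacy objectives assessing efficacy after the first dose". Protocol Table 9 repeats it.

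Both documents allocate the SAS by what was given. In SAP 9.6, "subjects are analyzed in the group they actually received"; in Protocol 10.2, "subjects will be analyzed in the group they actually received". SAP 9.6 then covers a person who received both CVnCoV and placebo, whether at different vaccinations or the same one: "subjects are analyzed in the active vaccine group for" as-treated purposes.

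The intent-to-treat rule is written for other sets: "in the Efficacy Sets and Per-Protocol Sets, subjects are analyzed in the group to which they were randomized". The SAS is not among them. SAP 9.6 does foresee an alternative. Depending on how many subjects were not treated as randomised, selected efficacy analyses "may be repeated on the SAS, analyzing subjects under the treatment they were actually randomized to".

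SAP Table 11 starts follow-up for this endpoint at the first vaccination. SAP 12.6.3.3 says there is no confirmatory testing of it.

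**The concern.** A VE estimate draws its protection against confounding from comparing the groups as they were randomised. This endpoint loses that protection only because it borrows a safety set together with that set's allocation rule. For safety, counting any exposure to the active product as active is a cautious choice. For efficacy it has no such justification.

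The mixed-recipient rule is the sharper part. It classifies a subject for the whole of follow-up by something that may happen only at dose 2, about four weeks after the clock starts. What is at stake is the interpretability of one secondary estimate. No success criterion depends on it.

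**Working it through.** **Reading the rules together.** Take a subject randomised to placebo who receives placebo on Day 1 and, by mistake, CVnCoV on Day 29.

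1. Entry: at least one dose and seronegative at baseline, so the subject is in the analysis (SAP 9.6.1, 12.6.3.3).
2. Clock: starts on Day 1 (SAP Table 11).
3. Group: CVnCoV for all of follow-up (SAP 9.6).
4. Result: Day 1 to Day 29, and any first case in that period, are credited to CVnCoV although none had been given.

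The reclassification may also depend on outcome. After COVID-19 between doses, Protocol 6.4 and 8.1 allow dose 2 only after two symptom-free weeks and within the visit window, which is -3/+7 days in Protocol Table 3. A subject with an early case is therefore less likely to reach dose 2 and change group. That favours CVnCoV in the early period, whereas counting unprotected mixed recipients as vaccinated works against it.

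**The plan's figures.** None is stated for this endpoint. The 90% power in SAP 8.7.1 belongs to the primary analysis. It reproduces closely (53 or fewer of 160 cases at p = 0.2857 gives 91.2% for the final look alone), but this point does not depend on it.

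**Illustration of size.** From the documents: 18,250 subjects per arm, 1:1 allocation, and VE 60% (SAP 8.7.1, assumed there for the two-dose endpoint and borrowed here); about 5% seropositive at baseline (Protocol 5.1.2). My assumptions: a share m of the placebo arm is mixed; their risk is k times that of an average placebo subject throughout; follow-up is equal. Incidence and follow-up length cancel.

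- As randomised: VE = 1 - 0.4 / (1 - m + mk)
- As treated: VE = 1 - (0.4 + mk) / (1 + m)
- Subjects affected: 18,250 x 0.95 x m

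| m | Subjects | k | As randomised | As treated |
|---|---|---|---|---|
| 0.1% | 17 | 1 | 60.0% | 59.9% |
| 0.1% | 17 | 3 | 60.1% | 59.7% |
| 0.5% | 87 | 1 | 60.0% | 59.7% |
| 0.5% | 87 | 3 | 60.4% | 58.7% |
| 1% | 173 | 1 | 60.0% | 59.4% |
| 1% | 173 | 3 | 60.8% | 57.4% |
| 1% | 173 | 0.4 | 59.8% | 60.0% |

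Example for m = 1%, k = 3: as randomised 1 - 0.4/1.02 = 60.8%; as treated 1 - 0.43/1.01 = 57.4%. The gap is about 3.4 points. In the k = 3 rows the extra risk sits only in the placebo arm, which is why the as-randomised value rises above 60%. In the last row mixed recipients have the full 60% protection, and the as-treated value is the higher one.

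**The case against.** The strongest reply is that the plan already sees the issue and that little rests on it. SAP 9.6 provides for an as-randomised repeat. SAP 12.1 tabulates, for all randomised subjects, how many received an incorrect vaccine at either vaccination, and lists them, so a reader can judge whether it matters. The endpoint is not confirmatory, the as-treated rule comes from the Protocol, and random errors dilute an as-randomised VE, so neither analysis is free of distortion. All of this stands. What remains is that the repeat is permissive, with no threshold and no endpoint named, so the comparison that follows randomisation may never be produced.

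Four stronger readings are tempting, and the documents do not support them:

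- **That an unblinded team decides on the repeat.** SAP 8.8 and 6.1 say the CRO team and some sponsor staff were unblinded at the final primary analysis, and that version 5.0 was written by an unblinded team. No text says who decides or when, and the change log for version 5.0 does not list this rule as new.
- **That several endpoints are affected.** SAP Table 3 still shows other efficacy rows on the SAS, but SAP 6.2 lists those endpoints as not analysed. One live endpoint remains.
- **That this analysis is the plan's check on the Efficacy Analysis Set (EAS).** It is less selected than the EAS, but neither document gives it that role, and it covers a different risk period.
- **That randomly swapping a share of each arm measures the bias.** That arithmetic gives the dilution of an as-randomised estimate and says nothing against the as-treated one.

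**Conclusion.** The point holds as a minor one. For VE after the first dose, the planned analysis is as treated, mixed recipients count wholly as CVnCoV although the clock starts at dose 1, and the as-randomised version is discretionary.

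The effect cannot be sized, because neither document gives the number of wrongly treated subjects. Under the stated assumptions the two analyses differ by less than 0.4 points if 0.1% of the placebo arm is mixed. They differ by about 3.4 points only if 1% is mixed, all unprotected and at three times the average risk. The difference is likely small if errors are rare, and its direction is not fixed. The primary and key secondary analyses use the EAS as randomised and are unaffected.

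**What to change.** For this endpoint, make the as-randomised analysis the main one (all subjects with at least one dose and seronegative at baseline), and present the as-treated analysis as sensitivity. At minimum, make the as-randomised repeat mandatory and name the endpoint.

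Amend SAP 9.6 and 12.6.3.3. Because Protocol 10.2, 10.2.1 and Table 9 set the current choice, record the change as a divergence in SAP 6.2.

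The cost is one treatment variable and one extra table; the subjects concerned are already counted and listed under SAP 12.1. SAP 12.6.3.3 assigns this endpoint to the interim and primary efficacy deliveries, and SAP 6.2 plans no efficacy analysis at end of trial. Where outputs have already been delivered, the change therefore needs a rerun, labelled as added after unblinding. If few subjects were wrongly treated, the two tables will agree and the question closes.
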